NIHR150393: Exploring and grouping COVID-19 pharmaceutical interventions to determine mechanisms of action and endotypes of response

This project is funded by the NIHR Efficacy and Mechanism Evaluation (EME) Programme (NIHR150393). The views expressed in this protocol are those of the author(s) and not necessarily those of the NIHR, NHS England or the Department of Health and Social Care

1 Research design

This research project is designed to identify the biological mechanisms through which novel COVID-19 drugs provide therapeutic benefit using data obtained from the ACCORD clinical trial(1). We will compare three novel therapeutics (Bemcentinib, Tozorakimab (previously known as MEDI3506) and Zilucoplan) to the Standard of Care (SoC) for severe COVID-19 patients using multiple data types (transcriptomics, proteomics, viral load, and pharmacokinetic drug levels). Each COVID-19 drug will be compared to the SoC of care individually before comparing the identified biological mechanisms comparatively to compare the mechanisms and conditions being modulated favourably by these drugs. Additionally, we will explore biological mechanisms and differences and relationships to effect size of clinical response as measured by time to improvement or discharge. This will better help us understand how the novel drugs work and how to select efficient treatments for a particular patient

1.1 Study Population

The inclusion criteria for the ACCORD trial were:

Adults (>= 18 years) with SARS-CoV-2 infection confirmed by laboratory tests and/or point of care tests. Patients must be scored between Grade 3 (hospitalised – mild disease, no oxygen therapy) to Grade 5 (hospitalised - severe disease, non-invasive ventilation or high flow oxygen) on ACCORD's 9 point WHO ordinal scale from clinical improvement (OSCI) where Grade 0 is uninfected and 8 is death. Overall, in the ACCORD study 167 subjects were randomised, 14 subjects withdrew and 25 subjects died. In the additional Bemcentinib study, a further 115 were randomised – 60 to SoC and 55 to Bemcentinib in an identical study design.

1.2 Sampling.

Samples from patients were collected in line with the sample collection schedule below:

	Baseline								
Day	1	3	4	5	8	10	11	15	29
Biological sample type									
Blood (for RNA)	Х			Х		Х			
Blood (for serology)	Х							Х	
Blood (for protein)	Х			Х		Х			
Oropharyngeal swab (for viral load)	Х	Х		Х	Х		Х	Х	Х
Pharmacokinetic drug concentration									
Bemcentinib	Х		Xa		Х			Х	
Tozorakimab	Xb							Xc	
Zilucoplan	Х			Х		Х		Х	

Table showing the sample collection schedule for the ACCORD COVID-19 clinical trial.

Adapted from (1) to show only the samples collected to generate the datasets relevant to this current project. X = sample collected. All patients were sampled on day 1, which is considered baseline prior to the first dose of the assigned treatment arm or standard of care. Each drug had slightly different pharmacokinetic (PK) sampling regimes and were mostly collected predose. Where samples for PK were collected other than pre-dose, collection information is detailed below:

- ^a Sample collected pre-dose and 6 hours post-dose (Day 4).
- ^b Sample collected pre-dose and 15 minutes post-dose (Day 1).
- ^c Sample collected pre-dose and 15 minutes post-dose (Day 15).

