2.2 Comparison and confounding of baseline clinical characteristics

Baseline clinical characteristics, including age, sex, ethnicity, significant comorbidities, laboratory results and clinical observations will be recorded, assessed and compared between patients in different treatment arms using R (v 4.1.2). Patient statistics tables will be calculated to test for any significant confounding variables between blinded groups. Principal component analysis of normalised expression values will be correlated with axes of variation e.g. ethnicity, to identify clusters affecting gene expression.

Differential gene expression analysis will control for baseline factors that may skew analysis by updating the statistic model design in DESeq2. Differential splicing analysis will be subject to weighting by multinomial covariate-balanced propensity scores to control for baseline confounding factors, as implemented by the R package Weightlt version 0.12.0, using the "just-identified" approach. Proteomics models will incorporate weighted baseline clinical data to avoid bias.

2.3 Transcriptomic analysis

The focus of this study will be the analysis of the transcriptomics dataset comprising patient data taken at three time points for three novel drugs and the SoC trial arm. The RNA-Sequencing samples have been generated and the raw FASTQC data have been downloaded from the ACCORD clinical trials platform. These data have been subject to quality control as previously described in the methods section. To avoid any unintentional bias, the groups will be blinded so that the bioinformatician will not know which patient group or SoC arm is which. The novel drug and SoC arms will be given a random identifier such as A, B, C or D for the duration of this analysis.

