functional relationships we wish to extract via the modelling exercise have similarities to what is acquirable from prior knowledge of other archived data. For example, Bepler & Berger (2021) and Rives et al. (2021), show how models trained on very large protein sequence data capture evolutionary and structural constraints of biology and can be used in subsequent benchmark downstream tasks such as predicting homologous relationships and secondary structures, outperforming models that are trained on the available small datasets alone(10,11). Here, we expect to build on these developments and use existing multi-omics data archived in public repositories to derive usable prior knowledge in models which could help alleviate the issues arising from the small amounts of data we have. Additionally, we will use leave-one-out cross validation, whereby models are trained repeatedly, leaving only a single datum out, and quantifying any inference we draw as averages over the left-out data. This way, statistically meaningful confidence can be derived on any inference we make -- the best one could do when in a limited data setting

References:

- 1. Wilkinson T. ACCORD: A Multicentre, Seamless, Phase 2 Adaptive Randomisation Platform Study to Assess the Efficacy and Safety of Multiple Candidate Agents for the Treatment of COVID-19 in Hospitalised Patients: A structured summary of a study protocol for a randomised. (2020). *Trials*. 21(1). doi:10.1186/s13063-020-04584-9
- 2. Ainsworth M. Performance characteristics of five immunoassays for SARS-CoV-2: a head-to-head benchmark comparison. (2020). *Lancet Infect Dis.* 20(12):1390–400. doi:10.1016/S1473-3099(20)30634-4
- 3. Love MI. Moderated estimation of fold change and dispersion for RNA-seq data with DESeq2. (2014). *Genome Biol.* 15(12):550. doi:10.1186/s13059-014-0550-8
- 4. Langfelder P. WGCNA: An R package for weighted correlation network analysis. (2008). *BMC Bioinformatics*. 9(1):559. doi:10.1186/1471-2105-9-559
- 5. Shannon P. Cytoscape: A software Environment for integrated models of biomolecular interaction networks. (2003). *Genome Res.* 13(11):2498–504. doi:10.1101/gr.1239303
- 6. Hänzelmann S. GSVA: Gene set variation analysis for microarray and RNA-Seq data. (2013). *BMC Bioinformatics*. 14(1):1–15. doi:10.1186/1471-2105-14-7/FIGURES/7

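### The protocol does not say whether the additional bemcentinib study is in the data; if it is, one unadjusted SoC group mixes two separate randomisations

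*Protocol*

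**What the plan says.** Section 1.1 (Study Population) describes two randomisations. The first is "in the ACCORD study 167 subjects were randomised", with no split by arm. The second is introduced by "In the additional Bemcentinib study, a further 115 were randomised" and allocated "60 to SoC and 55 to Bemcentinib in an identical study design". It has no tozorakimab or zilucoplan arm.

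The analysis sections treat SoC as one group:

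- Section 1 (Research design): "Each COVID-19 drug will be compared to the SoC of care individually".
- Section 2.3 (Transcriptomic analysis): the dataset covers "three novel drugs and the SoC trial arm", and "The novel drug and SoC arms will be given a random identifier such as A, B, C or D".
- Sections 2.3.1 and 2.4: gene expression and proteins are compared between each treatment and SoC, with no mention of the study from which the controls come.

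On adjustment, Section 2.2 plans control for baseline factors in DESeq2, propensity weighting for splicing and baseline weighting for proteins. Section 2.4 adds correction of protein batches that show up on PCA plots. None of these names source study.

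On data source, Sections 1, 1.2, 1.2.1, 2.3 and 2.4 all attribute the samples or data to ACCORD. The additional study is neither included nor excluded by name.

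**The concern.** Randomisation makes arms comparable only within the study that carried it out. The 60 SoC patients of the additional study were randomised against bemcentinib alone. If they are merged into the common SoC group, any difference in expression level between the two studies, whatever its cause, appears in the tozorakimab and zilucoplan contrasts as though it were a drug effect.

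The between-drug work is exposed too. Bemcentinib would draw on both studies and the other two drugs on ACCORD only. Comparing bemcentinib with either of them in the between-drug expression models (2.3.1), the module-to-arm associations (2.3.2) or the multigroup splicing analysis (2.3.4) would then be partly a comparison of studies. Grouping the drugs by mechanism is the project's stated purpose, so this matters. Multiple-testing correction does not remove a bias of this kind.

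**Working it through.** **1. The protocol's own counts.** 60 + 55 = 115, as stated. Total randomised: 167 + 115 = 282. Sequenced samples (Section 1.2.1.1): 286 − 14 = 272, as stated.

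**2. Do the sample counts settle whether the additional study is included?** RNA was planned at three visits (days 1, 5 and 10).

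- ACCORD alone: 167 × 3 = 501 possible samples; 286/501 = 57%.
- Both studies: 282 × 3 = 846 possible samples; 286/846 = 34%.

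Both are possible, so the counts do not decide the matter.

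**3. Which contrasts are exposed if both studies are used?**

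| Contrast | Uses additional-study patients? |
|---|---|
| Tozorakimab or zilucoplan, pre versus post treatment | No |
| Tozorakimab or zilucoplan, responders versus non-responders | No |
| Tozorakimab or zilucoplan versus SoC | Yes, up to 60 SoC |
| Bemcentinib versus tozorakimab or zilucoplan | Yes, up to 55 bemcentinib |
| Module-to-arm association; multigroup splicing | Yes |

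**4. Illustration of size.** The number of ACCORD SoC patients, s, is not given; assume 30 to 60. Assume also that samples from the two SoC groups are included in proportion. The additional study's share of pooled SoC is f = 60/(60 + s):

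- s = 60: f = 60/120 = 0.50
- s = 30: f = 60/90 = 0.67

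If a gene's mean differs between studies by d (in SD units) and the drug does nothing, the unadjusted tozorakimab or zilucoplan contrast with pooled SoC is off by f × d. With d assumed to be 0.2 to 0.5:

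| d | f = 0.50 | f = 0.67 |
|---|---|---|
| 0.2 SD | 0.10 SD | 0.13 SD |
| 0.5 SD | 0.25 SD | 0.33 SD |

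**5. False positives.** These depend on absolute numbers as well as on f. Under a normal approximation, with all SoC patients included and an assumed 30 to 42 patients in the drug arm, a two-sided 5% test has a standard error of √(1/n_drug + 1/(60 + s)). Its error rate per affected gene would be about 8% to 11% at d = 0.2 and 23% to 43% at d = 0.5. This is a full-inclusion case. At three visits each, 90 to 120 SoC patients would need 270 to 360 samples, against 286 sequenced in total, so the numbers per visit must be smaller and the inflation less. The bias in step 4 depends only on the share f and is unaffected.

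**The case against.** The strongest reply is that pooling is never stated. The protocol repeatedly calls its data ACCORD data, and a singular SoC arm with four labels is just what an ACCORD-only dataset would have. This stands. A reader might infer from Section 1.1 that the 60 patients are certainly in the SoC group, but the text does not establish it. The evidence for inclusion is that the additional study is listed under Study Population, that Section 1.2.1.2 says the protein panel was run in the study population, and that no other reason for listing it is given. That makes inclusion a fair possibility and leaves an ambiguity that the protocol itself should resolve.

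A second reply is that the list of adjustment factors is open and model terms are commonly left to a SAP. This stands in part: source study could still be added. But the protocol itself fixes the group structure and the masked labels, and the baseline factors it lists are patient characteristics. The Mann-Whitney tests it expects to use for proteins cannot carry a covariate.

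A third reply is that the two designs are identical. That describes the design. It does not make patients from one randomisation exchangeable with those from another. Equally, the document reports no actual difference between the studies in time, sites, care or laboratory runs.

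Two further inferences are tempting and unsupported. One is that masking hides the source study from the analyst: Section 2.3 masks the treatment group and does not say that study, site or batch is withheld. The other is that a platform-stage term is needed: the only basis is the cited title, "Seamless, Phase 2 Adaptive Randomisation Platform Study", and the protocol describes no stages in its own data.

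**Conclusion.** The point holds conditionally. As written, the plan has one SoC group, two randomisations in its study population, and no source-study term or same-study restriction. If the additional study's samples are in the data, following the plan mixes study differences into the tozorakimab and zilucoplan contrasts with SoC and into comparisons of bemcentinib with the other two drugs. If they are not, the analysis is unaffected and only the description needs correcting.

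The claim concerns at most the 60 additional SoC patients and the 55 bemcentinib patients. ACCORD's own SoC patients are not in question, and neither are the within-arm contrasts for tozorakimab and zilucoplan. The figure of about 0.10 to 0.33 SD is illustrative. It rests on an assumed 30 to 60 ACCORD SoC patients, proportional inclusion and an assumed shift of 0.2 to 0.5 SD, none of which the protocol gives.

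**What to change.** First, state which study's samples enter each dataset, with SoC numbers by study. If only ACCORD is used, say so in Section 1.1 and stop there.

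If both are used:

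- Put source study as a fixed factor in the DESeq2 and limma models.
- Account for it in the splicing analysis. Weights can balance study only between bemcentinib and SoC, because no tozorakimab or zilucoplan patient belongs to the additional study. For those two drugs use a covariate or restrict the controls.
- For proteins, use a study-stratified rank test or same-study controls. For tozorakimab and zilucoplan the two come to the same thing, since the additional study's stratum holds no patient on either drug.
- Carry a masked study label beside A to D.
- Report tozorakimab and zilucoplan against ACCORD SoC only, as the main or a sensitivity analysis. This is useful even with the study factor in place, because an additive model still borrows from the additional study on the assumption that the bemcentinib effect is the same in both.

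The cost is one model term and one label, with fewer effective controls and so wider intervals for tozorakimab and zilucoplan.

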1.2.1 Datasets

The datasets generated from the above sampling protocol of the ACCORD trial include transcriptomics, proteomics, viral load, serology, pharmacokinetic drug concentration and clinical laboratory datasets. Further information about the generation and processing of each dataset is outlined below:

1.2.1.1 Transcriptomic dataset (RNA Sequencing)

Sequencing was performed on patient blood samples taken on days 1 (at baseline prior to treatment), day 5 and day 10 of admission to hospital. A total of 286 samples were sequenced using an Illumina NovaSeq 600 platform. Total RNA was prepared from blood and depleted of highly abundant transcripts for alpha and beta haemoglobin and ribosomal RNA. No more than 50 samples per 'lane' were multiplexed to maximise sequence read depth to ensure a minimum sample read depth of 100 to 150 M. Quality control (QC) of raw read data was performed using FastQC version 0.11.9 and compiled and visualised using MultiQC version 1.12. Samples with <20 million total reads and less than 50% of the total read count were excluded from further analysis. After MultiQC analysis, fourteen sample were removed that failed quality control, leaving 272 high-quality samples available in the transcriptomic dataset for downstream analysis.

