1.2.1.2 Proteomic dataset (Luminex)

A Bio-Plex Pro Assay kit was utilised to assess the concentrations of cytokines, chemokines and growth factors in the study population from samples taken on days 1 (pre-treatment), 5 and 10 of admission. The 27 cytokines, chemokines and growth factors measured are: IL-1 β , IL-1ra, IL-2, IL-4, IL-5, IL-6, IL-7, CXCL8/IL-8, IL-9, IL-10, IL-12p70, IL-13, IL-15, IL-17A, Eotaxin, Basic FGF, G-CSF, GM-CSF, IFN- γ , IP-10, CCL2/MCP1, CCL3/MIP-1 α , CCL4/MIP-1 β , PDGF-BB, CCL5/RANTES, TNF- α and VEGF. Following analysis of each batch, 27 reports (one for each analyte) containing the assay results (in pg/ml) were generated using the xPONENT for MagPix software and saved within the study specific electronic file. A CSV file will be generated and exported for further analysis.

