Missing data will be minimised, with outcomes collected after premature withdrawal of treatment. The primary clinical estimate will be analysed using a treatment policy strategy. If an OSS is missing on a particular study day, the unscheduled visits will be considered to see whether there was an unscheduled visit on that day. If so, the score from the unscheduled visit will be used. For the purposes of the primary analysis patients who died or were transferred will not be censored at day of death/transfer, time to clinical response will instead be censored as 29 days. Patients are considered to be in the study until Day 29 but a score of 8 will be imputed for the OSS for those who died from their date of death and for all subsequent visits. Moreover, if a patient withdraws and then dies and we have a record of their death then a score of 8 will be imputed from their date of death onwards for all analyses. For those who transferred, additional data post transfer has been collected and will be used. If a patient is discharged, has no Day 29 value but has a day 60 value they will be considered Alive for the mortality analysis and Last observation carried forward (LOCF) will be used to impute Day 29. If a patient has discharged and no additional data are available, then they are assumed alive at Day 29 and LOCF will be used to impute Day 29 value. If the OSS is missing on the date of discharge, this will be imputed to 2 (most conservative value possible for discharged patients). If the OSS is \geq 3 on the date of discharge, then the score will be imputed to 2. If a patient is subsequently readmitted and has ordinal scale data, then this data will be used. However, if data has not been entered upon readmission, then the patient will be considered a non-responder for the primary endpoint. Once they have been discharged then if OSS is missing it will be imputed as 2 for subsequent days. Reported ethnicity will be compared with ancestral ethnicity inferred using genetics data (Peddy software) and mapping of genotypes to gnomAD v2.1.1 data. Inferred (genetic ancestry) will be preferred over reported ancestry where discrepancies occur. Sex will be calculated counting genotypes on the X chromosome and be used preferentially where gender may not match biological sex.

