2.3.1 Differential Gene Expression analysis

Firstly, we will conduct outlier analysis using data visualization methods such as Principal Component Analysis, Boxplots, Hierarchical Clustering and IQR/Median plots. After testing for potential outliers, non-specific filtering will be conducted on our dataset to remove any very lowly expressed genes. Differential expression testing will be conducted in R version 4.1.2 using the Bioconductor package DESeq2(3). The data will be normalized with the DESeq2 mean of ratios method and baseline characteristics will be controlled for using the function design(model). We will first compare, for each drug arm, differentially expressed genes at pre-treatment versus post-treatment to understand the biological pathways driving drug response. We will modify our analysis as results evolve to test for differences in gene expression and identify transcriptomic gene signatures for genes and/or pathways driving differences between responders and non-responders for each drug. We will then compare gene expression between each treatment and SoC. We will also build smaller models comparing Differentially Expressed Gene (DEG) analysis between drug groups.

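### Day 5 and Day 10 RNA and protein samples exist only for a selected part of the randomised patients, and the planned contrasts adjust for baseline factors without requiring the same patients before and after

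*Protocol*

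**What the plan says.** Section 1.2 states that "All patients were sampled on day 1, which is considered baseline". Section 1.2.1.1 places the later RNA samples at "day 5 and day 10 of admission to hospital", and section 1.2.1.2 describes the protein data as coming from "samples taken on days 1 (pre-treatment), 5 and 10 of admission". Section 1 measures clinical response by how quickly a patient improves or is discharged.

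On numbers, section 1.1 reports for ACCORD that "167 subjects were randomised, 14 subjects withdrew and 25 subjects died", and for the additional bemcentinib study that "a further 115 were randomised". Section 1.2.1.1 says "A total of 286 samples were sequenced", of which 14 failed quality control and 272 remain. No count by day or arm is given.

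On analysis, section 2.3.1 first compares, within each drug arm, "differentially expressed genes at pre-treatment versus post-treatment", then looks at responders against non-responders, and then at each drug against SoC. Section 2.3.4 plans pre/post and drug-versus-SoC contrasts for splicing. Section 2.4 plans drug-versus-SoC and responder contrasts for protein. Section 2.2 controls for baseline characteristics, through the DESeq2 design for expression, propensity weights for splicing and weighted baseline data for protein.

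Section 2.1, on missing data, opens with "Missing data will be minimised, with outcomes collected after premature withdrawal of treatment". It then gives rules for death, transfer, discharge and readmission, but only for the ordinal score. Its remaining rules concern ethnicity and sex. It has no rule for an absent Day 5 or Day 10 blood sample.

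**The concern.** Randomisation makes the arms comparable at Day 1. It does not do so for the patients who supply blood on Day 5 or Day 10, because treatment and prognosis can both influence who they are. Controlling for baseline factors does not remove selection that takes place after treatment starts.

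Two kinds of contrast are exposed. If the pre/post comparison sets all Day 1 samples against whichever samples exist later, it mixes a change in expression with a change in patients. This happens even when discharge and death are equal in every arm. The drug-versus-SoC comparison at Day 5 or Day 10 is exposed if the treatment alters who remains to be sampled. The project aims to assign mechanisms to drugs, so such a difference could be reported as a mechanism.

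**Working it through.** **Inputs from the protocol.** 167 randomised, 14 withdrawn, 25 died, and a further 115 randomised (section 1.1); three RNA sampling days (section 1.2); 286 samples sequenced and 14 removed (section 1.2.1.1).

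**Reproducing the stated figure.** 286 − 14 = 272, as stated.

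**How much is absent.**
- Scheduled for 167 patients: 167 × 3 = 501. Sequenced share: 286/501 = 57%. Absent: 501 − 286 = 215 (43%).
- If all 167 have a sequenced Day 1 sample, the later samples number 286 − 167 = 119 of 2 × 167 = 334, or 36%.
- Deaths and withdrawals, with no overlap and both later samples lost in every case, account for at most 2 × (14 + 25) = 78. That leaves at least 215 − 78 = 137 absent for other reasons: discharge, non-collection or no sequencing. The 25 deaths cover the whole study, so the number before Day 10 may be smaller.
- If the additional study is included: 167 + 115 = 282 patients, 282 × 3 = 846 scheduled, 286/846 = 34%. A sequenced Day 1 sample from all 282 would leave only 286 − 282 = 4 later samples, so on this reading some patients were very likely not sequenced at all.

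**What selection could do (illustration only).** The sampling shares and correlations here are assumptions; the protocol gives neither. Let a marker with SD 1 have correlation r with severity, and let only the sickest fraction p be sampled. The mean of the marker among those sampled is r × φ(z)/p, where z cuts off the upper fraction p. The ratio φ(z)/p is 0.798 at p = 0.50, 0.966 at p = 0.40 and 1.058 at p = 0.35.

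1. *Within an arm, later samples against all Day 1 patients.* At p = 0.50 the shift is 0.4 × 0.798 = 0.32 SD to 0.6 × 0.798 = 0.48 SD. At p = 0.40 to 0.35 it is 0.4 × 0.966 = 0.39 SD to 0.6 × 1.058 = 0.63 SD. There is no true change in the marker.
2. *Between arms, drug changes who leaves but not the severity that the marker tracks.* With p = 0.50 on SoC and 0.40 to 0.35 on drug, the false difference is 0.4 × (0.966 − 0.798) = 0.07 SD to 0.6 × (1.058 − 0.798) = 0.16 SD. The drug arm looks sicker.
3. *Between arms, drug lowers severity, with one common discharge threshold.* The same shares arise from a downward shift of 0.253 or 0.385 SD. The differences are 0.4 × (0.966 − 0.253 − 0.798) = −0.03 SD to 0.6 × (1.058 − 0.385 − 0.798) = −0.07 SD. The sampled drug patients now look slightly less sick.
4. *Equal p in both arms under the model of case 2.* The between-arm difference is zero, and the within-arm shift in case 1 remains.

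Cases 2 and 3 use the same sampling shares and give opposite signs. All four cases ignore deaths, which remove patients from the sickest end.

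**The case against.** The strongest reply is that the protocol is silent rather than wrong. Section 2.3.1 never says that the pre/post comparison is unpaired, and pairing and sample counts are often left to an SAP, which is not at hand. That is fair, and a reader should not infer that an unpaired analysis is planned. The point stands because this protocol carries its own analysis plan. It has a missing-data section that deals with death and discharge only for the ordinal score, and a confounding section confined to baseline factors. As written, the plan permits the problem.

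A reader might also infer that sampling stopped at discharge. The protocol does not say so. The phrase may simply date the samples, swabs are scheduled to Day 29, and section 2.1 refers to Day 60 values for discharged patients. Only dependence on being alive is certain.

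Nor do the documents support saying that responders with a Day 10 sample are only the slow ones. The response measure includes improvement as well as discharge, so a patient who improves early and stays in hospital is a prompt responder who can still be sampled.

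Finally, 501 is a product of the schedule and the number randomised. The protocol does not say that every scheduled sample was to be sequenced, so the shortfall cannot be attributed to discharge.

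**Conclusion.** The point holds in a limited form. Whether a patient has a Day 5 or Day 10 sample is decided after randomisation. It depends on survival and probably on still being in hospital, and the planned adjustment covers baseline factors only. With 57% of the scheduled RNA samples sequenced for 167 patients, the gap is too large to leave without a stated rule.

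It is tempting to go further and say that an effective drug would leave a sicker Day 10 group and so look ineffective or pro-inflammatory. The documents do not support that. The sign depends on the model assumed, between-arm bias needs the drug to alter who is sampled or how sick they are, and no counts by arm and day are available. The SD figures above show what is possible under assumed shares and correlations; they do not estimate the bias in this study. The risk to an unpaired pre/post contrast is the firmer part, since it does not need the arms to differ.

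**What to change.** In section 2.3.1, and in the matching splicing and protein contrasts of sections 2.3.4 and 2.4:

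- Run pre/post analyses only in patients with their own Day 1 sample, with patient as a blocking term or random effect.
- Base drug-versus-SoC contrasts at Days 5 and 10 on change from Day 1 (arm-by-time interaction), or adjust for the Day 1 value.
- Tabulate samples by arm and day with the reason for absence: discharged, died, withdrawn, not collected, not sequenced, failed quality control.
- State Day 5 and Day 10 findings as conditional on being alive and sampled, not as randomised treatment effects. Pairing removes the change of patients from the pre/post contrast; it does not make those sampled representative of all randomised.

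Weighting by the inverse probability of being sampled is at most a sensitivity analysis, and only where discharged patients had some chance of being sampled. If they had none, the weights are undefined for them, and no weighting recovers expression in patients who have died. The weights could also be unstable: 119 later samples spread evenly over four arms and two days is 119/8, or about 15 per cell. Naming Day 5 as the main time point would be a preference; this point does not require it.

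The cost is some wording, a changed model formula and one table, with no new data. Unpaired samples drop out of the change analyses and the conclusions become narrower.
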